NGO: Non-Governmental Organization

PCL: Post-Traumatic Stress Disorder

Checklist

Checklist for DSM

PHQ: Patient Health Questionnaire

PM+: Problem Management Plus

PP: Per Protocol

PSYCHLOPS: Psychological Outcome

Profile Instrument

PTSD: Post-Traumatic Stress Disorder

RAS: Refugees and Asylum Seekers

RCT: Randomized Controlled Trial

SH+: Self Help Plus

SOP: Standard Operating Procedure

UNHCR: United Nations High Commission for Refugees

WHO: World Health Organization

WHO CC: World Health Organization

Collaborating Center

WHODAS: WHO Disability Assessment

Schedule

RATIONALE AND BACKGROUND INFORMATION

Since the start of the war in Syria in 2011, more than 5 million Syrians had to take refuge in a safer place and they had chosen neighbouring countries including Turkey, Lebanon, Jordan, Iraq and countries in Africa including Egypt and North Africa (1). In the last years, the number of people who seek refugee status from European and bordering countries has gradually increased (9). As stated by the United Nations High Commission for Refugees (UNHCR), while there were only 8000 Syrians under temporary protection in Turkey by the end of 2011, Turkey hosts 3,635,841 registered Syrians under temporary protection as of the date of Februrary, 2019 (10;11). With more than 3 million Syrian refugees residing either in cities or refugee camps, Turkey hosts the highest number of refugees (12). Recent data do not demonstrate a decrease in the number of refugees in the short term, in fact, an increase is expected (13). In addition to that, there are 73.474 Arabic speaking people who applied to get international protection from Turkey in 2018 (65).

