The HTQ, developed by Mollica and colleagues is a self-report questionnaire with 4 parts. The purpose of part 1/A is to measure traumatic life events.

The PMLD checklist was used to assess the levels of stress due to typical post-migration stressors developed from discussions with immigrant and refugee communities in Sydney. The checklist asks respondents to rate their experience of the problems, during the last 12 months, on a five point scale ('was not a problem' to 'a very serious problem'). A high cumulative score indicates a high degree of post-migration stressors.

Randomization

Randomization will occur at individual level and will be stratified by recruiting centre. Randomization will be centralized and coordinated by the WHO Collaborating Centre (CC) of the University of Verona. Eligible participants will be randomly assigned to one of the two groups with an equal probability of assignment to each group (allocation ratio 1:1). The randomization schedule will be generated using the web-based software Castor Electronic Data Capture (47). This electronic tool employs a variable block randomization method, in order to allocate groups randomly permuted in blocks of unequal size. The site investigator will not know the block size. Members of the research team involved in the recruitment will be able to access the web-based software to randomize each new enrolled participant, but will not be able to access the randomization list. In addition, the web-based software will allow random allocation only after the main information on the enrolled participant is entered, upon verification of the inclusion criteria. After random allocation, the software will produce a unique identification number (ID) for each participant. Recruiting members of the research team will be able to access the web-based software to randomize each new enrolled participant and will be immediately informed about the allocation arm, but will not be able to access the randomization list. The randomization list will be accessible only to the data manager.

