On the basis of data extrapolated from prevention trials, it is expected an event rate (psychiatric diagnosis) of around 15% at six months (primary outcome) (48;49). However, these prevention trials were conducted in unselected populations that were not exposed to migration stressors. By contrast, refugees are exposed to pre-migration, migration and post-migration chronic stressors that are associated with up to ten times increased rates of mental disorders (50). On these grounds, we anticipate an incidence rate of mental disorders of 25% at six months in this population. It is hypothesized that the provision of the SH+ programme will show a clinically significant advantage by producing a between groups absolute difference of 10%. A sample size of 500 participants (250 in each group), achieves 80% power for a 0.05 level of significance between the two proportions of people diagnosed with mental disorders at six months. Assuming that a relevant proportion of refugees might be lost at study endpoint (due to the specific characteristics of this population), the final sample size will be of 600 participants (300 in each group). All trial phases will be piloted before the fully powered randomized trial with approximately 3-4 refugees in order to check and harmonise all procedures.

Characteristics of the experimental intervention

The Self Help Plus (SH+) programme

SH+ programme has been developed by WHO and collaborators working in the humanitarian field, with expertise in global mental health and psychosocial interventions. SH+ programme consists of a pre-recorded audio course, complemented with bibliotherapy, and thanks to this format not requiring much time from experts for implementation. The potential of using a psychoeducational course to access hard-to-reach populations has been demonstrated previously (51). Evidence for bibliotherapy is also promising (52). Furthermore, research has found that guided self-help programs produce much better results than "pure" (unguided) self-help, and the effects produced by guided self-help are surprisingly similar to face-to-face psychological treatment (53). SH+ was designed to be relevant for large segments of adversity-affected populations: it is intended to be transdiagnostic, easily adaptable to different cultures and languages, and both meaningful and safe for people with and without mental disorders. WHO organized extensive peer-review, with 43 international experts reviewing the intervention.

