The statistical analysis will be masked. The trial statistician will be blinded to the treatment groups until the analysis has been completed. Moreover, the trial statistician will not be involved in determining participants' eligibility, in administering the intervention, in measuring the outcomes, or in entering data (data will be entered with a double-entry procedure). All analyses will be performed using Stata/SE, Release 14.2.

Two data locks will occur during the study. The first one will happen 6 months after the end of the 12-month enrolment period (month 18 from study beginning), when the information on the primary outcome and on the short-term secondary outcomes will be available for all study participants. The second one will happen at the end of the study (month 24 from study beginning), when information on the long-term secondary outcomes will be available for all participants.

All primary and secondary analyses will be performed on an intention-to-treat (ITT) basis. The ITT population will consist of all participants randomly assigned to the competitive intervention strategies. In order to check the robustness of results, the primary outcome will be additionally analysed using a per protocol (PP) approach, that will include only participants who fulfil the protocol in terms of eligibility, interventions, outcomes assessment at follow-

ups. The analysis of the PP population will be used for confirmatory purposes only. If less than 5% of participants does not receive the allocated intervention according to the study protocol, the PP analysis will not be performed.

All analyses reaching statistical significance will be replicated for each recruiting centre and for each population group separately. In addition, all analyses reaching statistical significance will be stratified by methods of assessment (face to face versus telephone or secure online audio/video communication).

Analysis of the primary outcome

The proportion of participants with a psychiatric diagnosis at 6-months follow-up will be compared between the two groups through the chi-square test (primary analysis). A multivariate analysis (secondary analysis) will be performed through a Poisson regression model, with a robust error variance (57), to estimate relative risks directly and to explore the potential confounding effect of prognostic factors, and the interactions with treatment.

Analysis of the secondary outcomes

Secondary outcomes are:

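### Centre and population-group results are produced only after a significant overall result, and by separate analyses that do not test whether the effect differs

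*Protocol*

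**What the plan says.** The General approach subsection of the protocol's Statistical Analysis fixes the rule: "All analyses reaching statistical significance will be replicated for each recruiting centre and for each population group separately". The sentence after it applies the same significance condition to mode of assessment (face to face v remote).

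The related statements are these:

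- **Analysis of the primary outcome.** The main test is a chi-square comparison of the two arms, not split by centre. A secondary Poisson model with robust variance is to look at confounding by prognostic factors and at interactions with treatment. It carries no significance condition, and its factors are not listed. The same model is planned for the other binary outcomes, including dropout.
- **Analysis of the secondary outcomes.** GHQ-12, WHODAS 2.0, PHQ-9, WHO-5, PSYCHLOPS and PCL-5 are analysed by seemingly unrelated regression and mixed ANCOVA. No treatment interaction is mentioned.
- **Randomization and Setting.** Allocation is stratified by recruiting centre. Recruitment goes through one or more organisations, in Istanbul and other cities. The number of centres is not given.
- **Eligibility Criteria.** Syrians under temporary protection and other Arabic-speaking immigrants and asylum seekers are eligible. The term population group is not defined for analysis.
- **Sample size.** "A sample size of 500 participants (250 in each group), achieves 80% power for a 0.05 level of significance between the two proportions".

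**The concern.** The rule has two weaknesses.

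First, repeating a test inside each subgroup asks whether the effect is detectable there, not whether it differs from the effect elsewhere. The trial is sized only for the comparison of all participants together, so a fraction of the sample will often miss significance even when the effect is identical everywhere. A set of significant and non-significant centres then invites a conclusion about differences that the analysis has not tested.

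Second, the overall p-value decides whether subgroup results exist at all. If the effect is confined to one group, or runs in opposite directions, the average is diluted and the overall test tends to be non-significant. The centre and group breakdown is then not produced in the situation where it would be most informative.

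At stake are the statements about where and for whom SH+ works. The primary comparison is not affected.

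**Working it through.** **Inputs from the protocol (Sample size and power calculations).** Control event rate: "we anticipate an incidence rate of mental disorders of 25% at six months in this population". Absolute difference 10 points, hence 25% v 15%. Alpha 0.05, taken as two-sided because that reproduces the stated size. Evaluable 250 per arm, randomised 300 per arm, 1:1.

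**Assumptions.** The number and size of centres, and the shares of the population groups, are not given. Equal centres (2, 3 or 4) and several group splits are used to show the range.

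**Step 1: the plan's own figure.** With mean proportion 0.20:

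n per arm = [1.960 × √(2 × 0.20 × 0.80) + 0.842 × √(0.25 × 0.75 + 0.15 × 0.85)]² / 0.10² = (1.109 + 0.472)² / 0.01 ≈ 250.

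The stated 250 per arm and 80% power are reproduced.

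**Step 2: power in one centre.** With m per arm in a centre, power = Φ{[0.10 × √m − 1.109] / 0.561}.

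- 2 centres, m = 125: 51%
- 3 centres, m = 83.3: 36%
- 4 centres, m = 62.5: 28.5%

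If all 300 per arm were evaluable, these would be 58%, 42% and 33%.

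**Step 3: the same, given a significant overall result.** The rule applies only after significance, so the conditional figures are the relevant ones. They come from 200,000 simulated trials with 25% v 15% in every centre (125, 83 or 62 per arm per centre).

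| Equal centres | Each centre significant | All significant | At least one not | None significant |
|---|---|---|---|---|
| 2 | 60% | 32% | 68% | 11% |
| 3 | 44% | 6% | 94% | 13% |
| 4 | 33% | 0.7% | 99% | 17% |

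Cross-check: if all centres are significant, the overall test almost always is too. The third column should therefore be close to (Step 2 power)^k / 0.80. This gives 0.257/0.80 = 32%, 0.048/0.80 = 6% and 0.0066/0.80 = 0.8%, in agreement.

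For comparison, an interaction test at the 0.05 level would signal heterogeneity falsely in about 5% of such trials.

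**Step 4: two unequal population groups with the same true effect.** Given overall significance, with a 90/10 split the smaller group is significant in 17% of trials and both groups in 14%. With an 80/20 split the figures are 29% and 22%.

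**Step 5: how often the breakdown is triggered when effects differ.** Take two equal groups, 125 per arm each, control rate 25% in both.

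- Benefit of 10 points in one group, none in the other: the SH+ arm averages (15% + 25%)/2 = 20%. Power for 25% v 20% with 250 per arm is Φ{[0.05 × √250 − 1.960 × √(2 × 0.225 × 0.775)] / √(0.1875 + 0.16)} = Φ(−0.62) ≈ 27%. Simulation also gives 27%.
- Benefit of 10 points in one, harm of 10 points in the other: the average difference is zero, and the breakdown is triggered in about 5% of trials.
- Benefit of 20 points in one, none in the other: the average is the planned 10 points, and the breakdown is triggered in about 81%.

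**The case against.** Several points on the other side stand and limit the claim.

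- **Heterogeneity is not wholly ignored after a null result.** A reader might infer from the rule that it is. The Poisson models for the binary outcomes include treatment interactions without any significance condition, and the list of factors is commonly left to the SAP, which is not among the documents. What remains is that the one rule naming centre and population group makes their results depend on significance, and that no interaction is stated for the scales.
- **The protocol does not say how subgroup results will be read.** Replicated may mean no more than repeated. A reader might infer that a non-significant centre will be declared a failure, but the text does not say so. The rule makes that misreading likely without requiring it.
- **The number of centres is unknown.** With a single centre the centre part of the point disappears. Stratified randomisation and recruitment in several cities make more than one plausible, and the population-group part does not depend on it.
- **The size of the smaller population group cannot be taken from the Rationale.** A reader might divide its statement that "there are 73.474 Arabic speaking people who applied to get international protection from Turkey in 2018" by the count of registered Syrians. The first is one year's applications and the second a cumulative register. Other eligible immigrants are in neither, and recruitment runs through organisations and social media. No group share follows, and Syrian v other is itself only a reading of an undefined term.
- **The condition does not always block the breakdown.** When the average effect stays at 10 points, subgroup results are usually triggered (about 81% in the last case of Step 5).
- **Interaction tests have low power, and a very small group may have no events in one arm,** so that a ratio of relative risks cannot be estimated. This is right, and the fix must allow for it.

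**Conclusion.** The point holds as a defect in a stated rule. Centre and population-group results depend on the overall p-value and are obtained by separate analyses, in a trial with 80% power only for the comparison of all participants.

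With a homogeneous 25% v 15% effect, 250 evaluable per arm and 2, 3 or 4 equal centres, at least one centre would be non-significant in about 68%, 94% or 99% of trials with a significant overall result. In the other direction, with a 10-point benefit confined to one of two equal groups, the breakdown would appear in about 27% of trials.

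These sizes rest on assumed numbers of centres and group shares. They concern how supplementary results are likely to look. They do not show that a false claim will be made, and they leave the primary test, its error rate and the sample size untouched. The change is worth making because the remedy is simple and cheap.

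**What to change.** Replace the sentence with a rule that applies whatever the overall p-value:

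1. Define the population groups for analysis.
2. Report the treatment effect with a 95% interval by centre and by population group, for the primary outcome and for each scale.
3. Add treatment-by-centre and treatment-by-group terms to the planned Poisson and ANCOVA models where subgroup numbers allow estimation. Otherwise report the subgroup descriptively.
4. Label these analyses exploratory and make no claims of significance within a subgroup.
5. Treat mode of assessment in the same way.

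The cost is a change of wording and a few more model fits, with no new data and no change to the design. The downside is that the interaction tests will have low power: a non-significant interaction must not be read as proof of consistency, and the estimates with their intervals should carry the interpretation.

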SH+ programme has two components: a pre-recorded course and a self-help book. Pre-recorded audio material (locally adapted) is delivered across five 2-hour sessions and in groups of 10 to 40 people. In order to be in accordance with the cultural norms and the preferences of target community, single gender groups will take place. The audio material imparts key information about stress management and guides participants through individual exercises and small group discussions. A written facilitator guide helps briefly trained non-specialist facilitators to conduct the course using these audio materials. To augment the course materials, an illustrated self-help book reviews all essential content and concepts. The book contains more than 400 illustrations and conveys key points with minimal text. It was written to be useful both as a standalone product and as a key resource for those participating in the course (8). The format of SH+ is innovative in that it seeks to ensure that key intervention components are delivered as intended through the use of pre-recorded audio, without the burden of extensive training and supervision.

SH+ programme is based on acceptance and commitment therapy (ACT), a form of cognitive-behavioral therapy, with distinct features (54). ACT is based on the concept that ongoing attempts to suppress unwanted thoughts and feelings can paradoxically make these problems worse. Instead, it emphasizes learning new ways to accommodate difficult thoughts and feelings – primarily through mindfulness approaches – without letting them dominate, while guiding people to take proactive steps towards living in a way that is consistent with their values. ACT has been shown to be useful for a range of mental health issues (55) and has been used successfully in a guided self-help format (56). More specifically, SH+ includes ACT techniques that aim to reduce stress, live in accordance with ones values and to increase social support.

Delivery of SH+

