Control arm participants will receive routine social support and/or care according to ordinary practice and following local regulations. Additionally, they will receive baseline and followup assessments according to the study schedule, and information about freely available mental health services, social services and community networks providing support to people under temporary protection of Turkey and refugees, and NGOs' contact details. A member of the research team will preliminary inform local NGOs and community networks about this trial. The follow-up assessments will consist of interviews with members of the research team, and imply the creation of a supportive environment and a regular clinical assessment and the possibility of interacting with local NGOs' for receiving information on any issues related to social integration and support. However, as the control arm will include only participants without a psychiatric diagnosis, they will not be connected with mental health services, in order to avoid medicalization of their condition of psychological distress. In case some participants in the control group develop a mental health condition during the study, they will be connected with mental health services (as reported above).. In comparison, refugees that are excluded because of a diagnosis of a mental disorder will be actively connected to professional treatment and contacts with local mental health care services which will be facilitated by members of the research team (as reported above).

In this trial, in agreement with the regulations in Turkey, study participants will receive the same interventions provided to the local general population with the same psychological condition. People from the general population who are experiencing emotional distress but do not meet criteria for a diagnosis of mental disorder are usually provided with information on how to access health care services, including primary health care services and emergency services. Additionally, they are also referred to social support services, including social care facilities, charities, NGOs and other community resources. The NGOs that will take part in this study by referring potential participants from their beneficiries and providing logistic support will provide both informal and psychosocial support to the participants in the ETAU group. All these interventions will be offered to study participants at baseline and at each follow-up visit.

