- GHQ-12 post-intervention, at 6- and 12-months follow-up;
- Proportion of participants with a psychiatric diagnosis (M.I.N.I.) post-intervention and at 12 months of follow-up;
- WHODAS 2.0 post-intervention, at 6- and 12-months follow-up;
- PHQ-9 post-intervention, at 6 and 12 months of follow-up;
- WHO-5 Wellbeing index post-intervention, at 6 and 12 months of follow-up;
- PSYCHLOPS post-intervention, at 6 and 12 months of follow-up;
- EQ-5D-3L: at 6 and 12 months of follow-up;
- PCL-5 post-intervention, at 6 and 12 months of follow-up;
- CSSRI-EU (adapted) at 6 and 12 months of follow-up;
- Proportion of participants leaving the study early (dropouts).

Proportion of participants with a psychiatric diagnosis (M.I.N.I.) post-intervention and at 12 months of follow-up

The proportion of participants with a diagnosis of any mental disorder post-intervention and at 12-months of follow-up will be compared between the two groups through the chi-square test. A multivariate analysis will be performed through a Poisson regression model, with a robust error variance, to estimate relative risks directly and to explore the potential confounding effect of prognostic factors, and the interactions with treatment (57).

GHQ-12, WHODAS 2.0, PHQ-9, WHO-5 Wellbeing index, PSYCHLOPS, PCL-5 post-intervention, at 6- and 12- months of follow-up

For each questionnaire, in case of missing items, the Corrected Item Mean Substitution method (58), will be used (i.e. the item mean across participants weighted by the subject's mean of completed items), using information from subjects belonging to the same treatment arm for the same follow-up time.

The hypothesis that the experimental intervention has no effect on GHQ-12, WHODAS 2.0, PHQ-9, WHO-5 Wellbeing index, PSYCHLOPS, PCL-5 scores will be tested by performing seemingly unrelated regression (59), for each follow-up, controlling for baseline values. In case of joint statistical significance of the coefficients related to treatment status, the effect of treatment on each score will be evaluated through appropriate statistical methods for repeated measurements.

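### The 80% power and the 5% level of the primary chi-square test assume that sharing an SH+ group creates no correlation in outcomes, and the protocol makes no allowance for it

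*Protocol*

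**What the plan says.** The Randomization section sets the unit of allocation: "Randomization will occur at individual level and will be stratified by recruiting centre". The section on the SH+ programme then puts participants together: "Pre-recorded audio material (locally adapted) is delivered across five 2-hour sessions and in groups of 10 to 40 people". Groups are single-gender, facilitators run the sessions, and the audio "guides participants through individual exercises and small group discussions". For the comparator, the ETAU section says "Control arm participants will receive routine social support and/or care according to ordinary practice and following local regulations"; it describes no group sessions.

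The sample size section states that "A sample size of 500 participants (250 in each group), achieves 80% power for a 0.05 level of significance", for 25% against 15%. It then goes to 600 and attributes the increase to loss by study endpoint.

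For the primary outcome, the two proportions "will be compared between the two groups through the chi-square test (primary analysis"). The same plain test is set for the two secondary M.I.N.I. comparisons: the proportions diagnosed "post-intervention and at 12-months of follow-up will be compared between the two groups through the chi-square test". The accompanying Poisson model has a robust error variance but is not said to be clustered on SH+ group. No ICC, design effect or delivery-group term appears anywhere. The text on contamination concerns leakage between arms, which is a different matter.

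**The concern.** This is an individually randomised trial with grouping in one arm only. If people who share sessions, facilitators and discussions end up with more similar outcomes because of that shared delivery, the SH+ proportion varies more than a binomial proportion would. The chi-square test then understates the SH+ arm's variance. Two things follow. When the average risks are equal, the test declares a difference more often than 5% of the time. When SH+ works but works unevenly between groups, any test that does hold 5% has less power than the protocol states.

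The protocol itself fixes both the sample size and the primary test, so this is not a detail left open for a statistical analysis plan. There is also a loss that cannot be repaired later: if the assigned group is not recorded as the trial runs, no later analysis can allow for it.

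**Working it through.** **Inputs from the protocol.** Event rates 25% and 15%; level 0.05 (two-sided, the reading that reproduces the sample size); 250 evaluable per arm out of 300 randomised; SH+ groups of 10 to 40.

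**Assumed, not in the protocol.** ICC from shared delivery of 0.01 to 0.05, acting in the SH+ arm only; error rates taken at equal average risk.

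**Likely group size.** Recruitment lasts 12 months in the project summary and 10 months (months 9 to 18) in the project timetable. 300 SH+ participants over that time is 300/12 = 25 to 300/10 = 30 a month, or 12.5 to 15 per gender if the genders are equal in number. Groups of 10 to 15 are therefore a reasonable inference. Even attrition thins them to 10 × 250/300 = 8.3 and 15 × 250/300 = 12.5 evaluable.

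**Step 1: reproduce the stated power.** Pooled SE = √(2 × 0.2 × 0.8/250) = 0.03578. SE under the alternative = √((0.1275 + 0.1875)/250) = 0.03550. Power = Φ((0.10 − 1.96 × 0.03578)/0.03550) = 80.0%. The protocol's figure is right under independence.

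**Step 2: add clustering in the SH+ arm.** With m evaluable per group:

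- DE = 1 + (m − 1) × ICC
- True error of the chi-square test = 2 × [1 − Φ(1.96/√((1 + DE)/2))]
- V = (0.1275 × DE + 0.1875)/250
- Chi-square power = Φ((0.10 − 0.0701)/√V)
- Power of a test allowing for grouping = Φ(0.10/√V − 1.96)

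| m | ICC | DE | Chi-square error | Chi-square power | Power allowing for grouping |
|---|---|---|---|---|---|
| any | 0 | 1.00 | 5.0% | 80.0% | 80.4% |
| 8.3 | 0.01 | 1.07 | 5.4% | 79.7% | 79.3% |
| 12.5 | 0.02 | 1.23 | 6.3% | 79.0% | 76.9% |
| 12.5 | 0.05 | 1.58 | 8.4% | 77.6% | 71.8% |
| 25 | 0.02 | 1.48 | 7.8% | 77.9% | 73.2% |
| 40 | 0.05 | 2.95 | 16.3% | 73.5% | 55.8% |

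The last column uses the unpooled variance. With a pooled null variance the shortfall is larger (51% instead of 56% in the last row), so these are the milder figures.

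**Step 3: simulation.** Beta-binomial outcomes, 300 per arm, 250 evaluable. The candidate test is the difference in proportions with variance clustered on SH+ group and Satterthwaite degrees of freedom. Its error rate stayed close to 5%: 4.8% to 5.5% in the main run, and up to 5.8% with 8 groups at ICC 0.05 in a repeat run. Its power in the main run was:

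| Group size (number of groups) | ICC 0 | ICC 0.01 | ICC 0.02 | ICC 0.05 |
|---|---|---|---|---|
| 10 (30) | 80.2% | 79.1% | 77.2% | 73.6% |
| 15 (20) | 79.6% | 77.6% | 75.5% | 70.3% |
| 25 (12) | 79.4% | 75.2% | 71.7% | 63.7% |
| 40 (8) | 77.9% | 72.2% | 67.7% | 56.4% |

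The simulated chi-square error agrees with the formula: 8.6% for groups of 15 and 14.1% for groups of 40 at ICC 0.05, thinned.

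**Step 4: a case in which nothing goes wrong.** If the correlation comes only from who is in a group (gender-specific risks of 35% and 15%, ICC about 0.05, no effect of delivery), the simulated chi-square error is 5.0%.

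**The case against.** The case against is about size, and much of it stands.

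- **The ICC is assumed.** At the likely group sizes, an ICC of 0.01 to 0.02 moves the chi-square error only to between 5.4% and 6.3%, and leaves 79% to 77% power after allowing for grouping. Pre-recorded audio, one participant per family and a 6-month endpoint may all keep the ICC low.
- **The error inflation needs a particular null.** If SH+ affects no one, or groups differ only in composition, the 5% level holds. Inflation requires some groups to be helped and others harmed, with an average of zero. At 20% risk, ICC 0.05 implies a between-group standard deviation of √(0.05 × 0.2 × 0.8) = 9 points, and ICC 0.01 implies 4 points. The larger figure is demanding. The power point does not depend on this null.
- **Groups of 40 are an outer limit.** Single-gender groups, several cities and recruitment spread over 10 to 12 months make them unlikely throughout. Thinned to 33 evaluable, they give 14.5% error and 59% power.
- **Grouped support under ETAU is not ruled out.** The protocol describes none, but NGOs give psychosocial support in that arm. Treating ETAU participants as independent follows the protocol's description.
- **A clustered sensitivity analysis might be enough.** That is defensible if the ICC is tiny. It would leave the primary conclusion on a test whose error rate depends on an unstated assumption.

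The extra 100 participants are not a hidden allowance, because they are assigned to attrition. If all 300 per arm were analysed, power under independence would be 86.7%, but the error inflation depends on group size and ICC, not on the total.

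**Conclusion.** The concern holds in its conditional form. The arithmetic behind 250 per arm is correct, but it and the chi-square test both set the correlation induced by SH+ groups to zero without saying so. That the allowance is missing is certain; how much it matters depends on an ICC the protocol does not give.

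For the likely groups of 10 to 15 and an assumed ICC of 0.01 to 0.05, the effect runs from negligible to moderate: 5.4% to 8.4% error with the planned test, and 79% to 72% power with a test that allows for grouping (79% to 70% simulated with small-sample degrees of freedom). Over the whole stated range of 10 to 40, without thinning, the figures are 5.5% to 16% and 79% to 56%. The two secondary M.I.N.I. comparisons are exposed in the same way. This should be fixed before analysis; it does not invalidate the design.

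**What to change.** 1. Record each participant's assigned SH+ group prospectively and keep it for non-attenders, in line with intention to treat.
2. Make the primary test of the 6-month diagnosis one that allows for SH+ group. One option is the difference in proportions with variance clustered on group in the SH+ arm, ETAU participants independent, and Satterthwaite degrees of freedom. Keep the plain chi-square test as a sensitivity analysis, and cluster the planned Poisson model in the same way for the relative risk.
3. Use the same test for the M.I.N.I. comparisons at post-intervention and 12 months.
4. Restate the power as a range over stated ICCs and group sizes, leaving the total at 600.
5. Protect masking. The General approach section says "The trial statistician will be blinded to the treatment groups until the analysis has been completed", and the cluster structure shows which arm is which. Either lock the code on dummy data before group identifiers are linked, or have someone other than the masked statistician run it.

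**Cost.** Wording changes in three sections, one variable and one masking step. If the ICC is in fact 0, the proposed test loses under 1 point of power with 20 to 30 groups, about 1 with 12 and about 2 with 8. Inference of this kind is fragile with only 6 to 8 groups. The shortfall is disclosed, not removed: 80% power would need (1.96 + 0.84)² × (0.1275 × DE + 0.1875)/0.10² evaluable per arm. That is about 255 to 305 for groups of 10 to 15 after thinning, and about 442 for full groups of 40 at ICC 0.05.
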